8.6. Warnings and Precautions

Special warnings or precautions for the study drug, derived from safety information collected by the sponsor or its designee, are presented in the [IB](#). Additional safety information collected between IB updates will be communicated in the form of Investigator Notifications. Any important new safety information should be discussed with the subject during the study, as necessary. If new significant risks are identified, they will be added to the ICF.

8.7. Data Monitoring Committee

No independent Data Monitoring Committee is planned for this study. A study committee may be established and include the investigators or designees, the sponsor representatives (eg, medical monitor), and, when appropriate, ad hoc experts.

8.8. Product Complaints

The sponsor collects product complaints on study drugs and drug delivery systems used in clinical studies in order to ensure the safety of study subjects, monitor quality, and facilitate process and product improvements.

All product complaints associated with material packaged, labeled, and released by the sponsor or its designee will be reported to the sponsor. All product complaints associated with other study material will be reported directly to the respective manufacturer.

The investigator or their designee is responsible for reporting a complete description of the product complaint via email or other written communication to the sponsor contact or respective manufacturer as noted in the packaging information. Any AE associated with a product complaint should be reported as described in Section 8.1.2 of this Protocol.

If the investigator is asked to return the product for investigation, they will return a copy of the product complaint communication with the product.

For Japan, complaints associated with unapproved medical devices will be reported to the sponsor with a Medical Device Defect Report Form, and the sponsor will report medical device defects to the PMDA as per local regulatory requirements.

9. STATISTICS

9.1. Study Populations

The efficacy evaluable population includes all subjects who received at least 1 dose of study drug.

The per Protocol (PP) population includes all efficacy evaluable subjects who were compliant with the Protocol.

The safety population includes all enrolled subjects who received at least 1 dose of study drug.

9.2. Selection of Sample Size

Approximately 46 subjects are planned for the final analysis of the primary endpoint of overall CR rate. With the assumed rates of 35% for the intervention, a sample size of approximately 46 subjects would provide > 80% probability to have a 95% confidence interval with lower limit of > 15% assuming 10% lost to follow-up.

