A sample of bone marrow aspirate or peripheral blood will be sent to the central laboratory for confirmation of FGFR1 rearrangement as well as a central pathology laboratory for analysis. In addition, sites will need to provide peripheral blood and bone marrow slides (core and aspirate whenever possible) at baseline and at the disease assessment timepoints and send them to a central pathology group for review.

Clinical Assessments:

Adverse event assessments, physical examinations, vital signs, ECGs, comprehensive eye examinations, ECOG performance status, and disease response assessments will be performed by the investigative site.

Estimated Duration of Participation:

Once the subject's eligibility has been confirmed through the site's laboratory, screening may begin. Up to 28 days are allowed for screening, followed by continuous treatment in consecutive 21-day cycles as long as the subject is receiving benefit (as judged by treating physician) and has not met any criteria for study withdrawal. Safety follow-up is 30 days (+ 5 days) after the last dose of the study drug. In addition, subjects will be followed for overall survival after stopping treatment with study drug. Study participation is expected to average approximately 6 months per individual subject.

Estimated Number of Subjects:

Approximately 46 subjects will be enrolled.

Principal Coordinating Investigator:

Statistical Methods:

Approximately 46 subjects are planned for the final analysis of the primary endpoint of overall CR rate. With the assumed rates of 35% for the intervention, a sample size of 46 subjects would provide > 80% probability to have a 95% confidence interval with lower limit of > 15% assuming 10% loss to follow-up.

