As of 16 APR 2023, in this study, 47 participants with hematologic malignancies received pemigatinib 13.5 mg QD on an intermittent and/or continuous schedule. All 47 participants (100%) had at least 1 TEAE. The most frequently occurring TEAEs ($\geq 50\%$ of participants) were HP (35 participants [74.5%]), diarrhea (29 participants [61.7%]), and alopecia (27 participants [57.4%]). A total of 28 participants (59.6%) had serious TEAEs. The only serious TEAEs reported in more than 1 participant were acute kidney injury (3 participants [6.4%]) and atrioventricular block complete and urinary tract infection (2 participants [4.3%] each). The following serious TEAEs were considered related to pemigatinib by the investigator and occurred in 1 participant (2.1%) each: alopecia, acute kidney injury, calciphylaxis, corneal abscess, erysipelas, HP, hypertransaminasemia, osteomyelitis, pain, pneumonia pseudomonas, and syncope. Four participants (8.5%) had a fatal TEAE. The fatal TEAEs were acute kidney injury, intervertebral discitis, malignant neoplasm progression, and multiple organ dysfunction syndrome (1 participant [2.1%] each). Six participants (12.8%) had a TEAE leading to pemigatinib discontinuation: blood ALP increased, cardiac failure, calciphylaxis, keratitis, lacrimation increased, and multiple organ dysfunction syndrome (1 participant [2.1%] each).

More information on the safety of pemigatinib can be found in the [IB](#).

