9.4. Statistical Analyses

9.4.1. Efficacy Analyses

9.4.1.1. Primary Efficacy Analyses

The primary endpoint of this study is the proportion of subjects who achieved a BOR of CR as determined by investigator assessment according to the response criteria for myeloid/lymphoid neoplasms with FGFR1 rearrangement (see [Appendix E](#)). This analysis will be based on the efficacy evaluable population. Subjects who do not have sufficient baseline or on-study response assessment information to be adequately assessed for response status will be included in the denominators in the calculation of overall response rate. The 95% CI for the proportion of subjects with CR will be estimated using the Clopper-Pearson method.

The proportion of subjects who achieved a BOR of CR will also be analyzed based on the PP population as a sensitivity analysis.

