^c The assessment of CR must be confirmed by a minimum of 2 bone marrow assessments only to confirm improvement in fibrosis. If there is no significant fibrosis present on the initial bone marrow biopsy, then a second biopsy is not required to prove resolution of fibrosis. Grading of fibrosis in measurement of treatment response should be according to the European Consensus System.

^d Resolution of abnormal peripheral blood counts must persist for at least 2 separate analyses over at least 8 weeks. In the case of proliferative disease, CR will include resolution of thrombocytosis to a normal platelet count ($150\text{--}450 \times 10^9/\text{L}$) and resolution of leukocytosis to $\text{WBC} \leq 10 \times 10^9 \text{ cells/L}$ but $\geq 1.5 \times 10^9/\text{L}$. Hemoglobin should be maintained $> 11 \text{ g/dL}$ and platelets $\geq 100 \times 10^9/\text{L}$ without the support of transfusions. Reduction in myeloid precursors (promyelocytes, myelocytes, metamyelocytes, nucleated red blood cells) to less than appreciable levels ($\leq 2\%\text{--}3\%$) and/or $1 \times 10^9/\text{L}$ monocytosis and/or eosinophils $\leq 0.5 \times 10^9/\text{L}$ in the absence of infection, cytokine treatment, or other reactive causes.

^e Transfusion dependency is defined by a history of at least 2 U of red blood cell transfusions in the past month for a hemoglobin level $< 8.5 \text{ g/dL}$ that was not associated with clinically overt bleeding. Cytopenias resulting from therapy should not be considered in assessment of progression.

^f Loss of cytogenetic burden of disease by (via FISH or classic karyotyping) is required to reach complete cytogenetic response. Decrease in the cytogenetic burden of disease must be by $\geq 50\%$ (via FISH or classic karyotyping) to be indicative of a partial cytogenetic response. Given variability of fluorescent probes used in FISH, cytogenetic normalization via FISH will depend on the performance characteristics of the specific probes used.

Table E2: Extramedullary Disease Response Criteria

Assessment	PET-CT Based	CT Based
CMR/CR		
Target	A 5PS score of 1, 2, or 3, w/ or w/o residual mass. Additionally, if screening FDG-PET scan is missing & on-study 5PS score is 1-3, then CMR is possible.	Nodal: < 1.5 cm in LDi. Extra-nodal: Absent.
Non-target		Absent.
New lesions	None.	
PMR/PR		

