3.3. Sample Size Considerations

Approximately 46 participants are planned for the final analysis of the primary endpoint of overall CR rate. With the assumed rates of 35% for the intervention, a sample size of approximately 46 participants would provide > 80% probability to have a 95% CI with lower limit of > 15% assuming 10% lost to follow-up.

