7.2. Analysis of the Primary Efficacy Parameter

7.2.1. Primary Efficacy Analysis

The primary endpoint of the study is the proportion of participants who achieve a BOR of CR as determined by investigator assessment according to the response criteria for myeloid/lymphoid neoplasms with FGFR1 rearrangement in [Appendix A](#). This analysis will be based on the efficacy evaluable population. Participants who do not have sufficient baseline or on-study response assessment information to be adequately assessed for response status will be included in the denominators in the calculation of CR rate. The 95% CI for the proportion of participants with CR will be estimated using the Clopper-Pearson method.

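### The probability above 80% stated for 46 subjects with 10% lost holds if the lost are dropped (82.4%), but the planned analysis keeps them as non-responders, which gives 73.2% if all are lost before CR

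*Protocol*

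**What the plan says.** Protocol 9.2 takes about 46 subjects and a 35% CR rate and concludes that this "would provide > 80% probability to have a 95% confidence interval with lower limit of > 15% assuming 10% lost to follow-up". The synopsis repeats it ("would provide > 80% probability to have a 95% confidence interval with lower limit of > 15% assuming 10% loss to follow-up"), as does SAP 3.3 ("would provide > 80% probability to have a 95% CI with lower limit of > 15% assuming 10% lost to follow-up"). None of the three says how the 10% enters the calculation, or whether the 35% is a rate among assessable or among all treated subjects.

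The analysis is specified separately:

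- Protocol 9.1: "The efficacy evaluable population includes all subjects who received at least 1 dose of study drug".
- Protocol 9.4.1.1: subjects without enough baseline or on-study response information "will be included in the denominators in the calculation of overall response rate". SAP 7.2.1 has the same rule and names the CR rate directly: such participants "will be included in the denominators in the calculation of CR rate".
- Both sections specify a 95% Clopper-Pearson interval for the CR proportion.
- Protocol 4.3.1 gives about 46 as the enrollment target, and 4.3.2 provides for no replacement, so no extra subjects are planned to cover losses.

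**The concern.** The sample-size statement and the primary analysis appear to treat lost subjects differently. A usual dropout allowance removes the lost subjects and calculates on those who remain. Here the analysis keeps them and gives them no CR. That lowers the expected CR proportion without reducing the denominator, so the number of CRs needed stays at the level set by 46.

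At stake is the plan's stated justification for its sample size. A reader would take it to mean that the probability of a lower limit above 15% stays over 80% even with 10% dropout under the analysis that will be run. If the figure rests on a different denominator, that reassurance is not supported.

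**Working it through.** **Inputs.** N = 46, CR rate 35%, loss 10%, lower limit above 15% (Protocol 9.2); two-sided 95% Clopper-Pearson interval (Protocol 9.4.1.1, SAP 7.2.1); all treated subjects in the denominator (Protocol 9.1 and 9.4.1.1, SAP 7.2.1).

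**Method.** For x CRs among n subjects, the Clopper-Pearson lower limit is the 2.5% quantile of Beta(x, n − x + 1). Let r be the smallest x whose lower limit exceeds 15%. The probability sought is P(X ≥ r) with X ~ Binomial(n, p).

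**Step 1: the plan's figure, with the lost subjects removed.** 46 × 0.9 = 41.4, so n = 41. The lower limit is 14.2% for 11/41 and 16.1% for 12/41, so r = 12. P(X ≥ 12 | 41, 0.35) = 82.4%. This reproduces the stated figure. In addition, 41/0.9 = 45.6 rounds up to 46, so this is probably how N was obtained.

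**Step 2: the specified denominator, no loss.** The lower limit is 14.3% for 12/46 and 16.0% for 13/46, so r = 13. P(X ≥ 13 | 46, 0.35) = 86.8%.

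**Step 3: the specified denominator, with loss before CR counted as non-CR.** If 35% applies to assessable subjects and a fraction L is lost before a CR can be recorded, the CR probability per treated subject is p = 0.35 × (1 − L). At L = 10%, p = 0.315.

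| Lost before CR (L) | p | P(X ≥ 13 of 46) |
|---|---|---|
| 0% | 0.350 | 86.8% |
| 5% | 0.3325 | 80.8% |
| 5.5% | 0.33075 | 80.1% |
| 6% | 0.329 | 79.4% |
| 10% | 0.315 | 73.2% |

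Solving P(X ≥ 13 | 46, 0.35(1 − L)) = 0.80 gives L = 5.6%.

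With a fixed number lost before CR, the calculation is P(X ≥ 13 | 46 − k, 0.35): 82.0% for k = 2, 79.1% for k = 3, 75.9% for k = 4 and 72.4% for k = 5.

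**Step 4: only some of the 10% lost before CR.** If half are, L = 5% and the probability is 80.8%. If three quarters are, L = 7.5% and it is 77.2%.

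**Step 5: at the number already treated.** Protocol 1.3.2 reports that by 16 APR 2023 "47 participants with hematologic malignancies received pemigatinib 13.5 mg QD on an intermittent and/or continuous schedule" in this study. At n = 47, r is still 13. The probability is 88.8% with no loss and 76.2% with 10% lost before CR.

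**Step 6: the FDA population (secondary).** SAP 5.3.1 limits the efficacy population for the FDA submission to participants with at least one prior systemic therapy. The documents do not give its size. Over an assumed range of n = 30 to 45 the probability moves in a saw-tooth. With no loss it runs from 64% to 87%, and is above 80% only at n = 34, 38, 39 and 41 to 45. With 10% lost before CR it runs from 48% to 75%.

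**The case against.** - **There is no miscalculation.** The stated figure is correct when lost subjects are dropped. That is so, but this is not the analysis the plan specifies.
- **The 35% may already be net of losses.** Protocol 9.2 attaches it to the overall CR rate, which the analysis sections define over all treated subjects. On that reading the probability is 86.8% and there is no shortfall. This stands as a possible reading. The text does not state it, however, and the 10% allowance would then have no function.
- **Lost to follow-up is not the same as unassessable for CR.** The endpoint is best response, so a subject lost after reaching CR still counts. This stands, and it makes 73% the lower end for a 10% loss and not an expected value. Some losses before CR are plausible, since Appendix E (Table E1, footnote d) requires that "Resolution of abnormal peripheral blood counts must persist for at least 2 separate analyses over at least 8 weeks". The documents do not say how many to expect.
- **Protocol 9.3 sets a one-sided 5% level.** A one-sided 95% Clopper-Pearson limit needs only 12/46 (lower limit 15.8%) and gives P(X ≥ 12 | 46, 0.315) = 82.8%. This does not rescue the statement. The sample-size text and the primary analysis both specify a 95% confidence interval, SAP 3.2 sets intervals at 95%, and SAP 7.1 lists no hypotheses.
- **Nothing downstream depends on the figure.** The CR rate will be reported with its exact interval whatever the planning sentence says. This is correct, and it limits the remedy to wording.
- **The FDA population is a separate matter.** SAP 9.1 discloses the restriction, and the sizes in Step 6 are assumed. This is fair; the main conclusion does not rest on it.

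**Conclusion.** The concern holds. The stated probability corresponds to dropping the lost subjects (82.4% at n = 41), whereas the specified analysis keeps all 46 and counts the unassessable as non-CR. Under that rule, with 35% as the rate among assessable subjects, the probability ranges from 86.8% with no loss before CR to 73.2% with all 10% lost before CR. It stays above 80% only if no more than about 5.5% are lost before CR.

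The size of the shortfall rests on two things the plan leaves open: which denominator the 35% refers to, and how many losses precede CR. If 35% is already the rate over all treated subjects, there is no shortfall, but the loss clause is then empty. The sentence needs correction on either reading. No analysis, formal decision or enrollment target is affected.

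**What to change.** In Protocol 9.2, the synopsis and SAP 3.3:

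1. State whether the 35% CR rate refers to assessable subjects or to all treated subjects.
2. If it refers to assessable subjects, replace the single probability with two: about 87% if all 46 are assessable, and about 73% if 10% are unassessable and counted as non-CR. If it refers to all treated subjects, give about 87% and remove the loss allowance.

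In SAP 3.3 only, add that the figure is for 46 participants and does not carry over automatically to the FDA efficacy population, and give the probability at that population's expected size.

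The cost is wording in three places. No extra patients are needed and the analysis does not change. The stated probability becomes a range with a less favorable lower end.

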9.3. Level of Significance

The level of significance for the primary endpoint is 1-sided 5%.

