The overall CR rate, defined as the proportion of subjects who achieve a best overall response (BOR) of CR as determined by investigator assessment, will be estimated with 95% CI. Likewise, the proportion of subjects who achieve response, defined as BOR of CR or PR, as determined by investigator assessment, the proportions of subjects who achieve BOR of CCyR and the proportion of subjects who achieve BOR of PCyR, as assessed by local analysis will also be estimated with 95% CI. The progression-free survival, duration of CR, duration of response, and overall survival will be analyzed by the Kaplan-Meier method. Descriptive statistics will be summarized for safety data and for the number of subjects with SD who achieve complete hematological response, marrow response, or clinical benefit, according to investigator assessment.

Data Monitoring Committee:

No independent Data Monitoring Committee is planned for this study. A study committee may be established and include the investigators or designees, the sponsor representatives (eg, medical monitor), and, when appropriate, ad hoc experts.

[figure not shown]
TABLE OF CONTENTS

TITLE PAGE	1
SYNOPSIS	3
TABLE OF CONTENTS.....	7
LIST OF ABBREVIATIONS.....	13
1. INTRODUCTION	16
1.1. Background.....	16
1.1.1. Fibroblast Growth Factor Receptor Inhibition in Oncology.....	16
1.1.2. Myeloid/Lymphoid Neoplasms With FGFR1 Rearrangement.....	17
1.2. Study Rationale.....	18
1.3. Potential Risks of the Treatment Regimen	19
1.3.1. Potential Risks of Pemigatinib Based on Preclinical Safety	19
1.3.2. Potential Risks of Pemigatinib Based on Clinical Safety	20
1.3.2.1. Pharmacokinetic/Pharmacodynamic Summary	22
1.3.3. Phototoxicity.....	25
2. STUDY OBJECTIVES AND ENDPOINTS.....	25
2.1. Study Objectives.....	25
2.1.1. Primary Objective.....	25
2.1.2. Secondary Objectives	25
2.1.3. Exploratory Objectives	25
2.2. Study Endpoints.....	25
2.2.1. Primary Endpoint.....	25
2.2.2. Secondary Endpoints	25
2.2.3. Exploratory Endpoints	26
3. SUBJECT ELIGIBILITY	27
3.1. Subject Inclusion Criteria	27
3.2. Subject Exclusion Criteria	28
4. INVESTIGATIONAL PLAN.....	30
4.1. Overall Study Design.....	30
4.2. Measures Taken to Avoid Bias.....	31
4.3. Number of Subjects	32
4.3.1. Planned Number of Subjects	32

4.3.2.	Replacement of Subjects.....	32
4.4.	Duration of Treatment and Subject Participation	32
4.5.	Overall Study Duration.....	32
4.6.	Study Termination	32
5.	TREATMENT	33
5.1.	Treatment Assignment.....	33

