3.2. Control of Type I Error

Unless otherwise specified, all CIs provided will be at the 95% confidence level.

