7.1. Efficacy Hypotheses

Not applicable.

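### Does the 1-sided 5% significance level in Protocol 9.3 conflict with the 95% confidence interval planned for the CR rate?

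*Protocol*

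**What the plan says.** Protocol 9.3 is a single sentence: "The level of significance for the primary endpoint is 1-sided 5" per cent. It names no hypothesis, reference value or test.

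The other statistical passages speak of an interval:

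- Protocol 9.2 sizes the trial on having more than 80% probability "to have a 95% confidence interval with lower limit of > 15" per cent, with an assumed CR rate of 35%, about 46 subjects and 10% lost to follow-up. SAP 3.3 repeats this: "probability to have a 95% CI with lower limit of > 15% assuming 10% lost to follow-up".
- Protocol 9.4.1.1: "The 95% CI for the proportion of subjects with CR will be estimated using the Clopper-Pearson method". SAP 7.2.1: "The 95% CI for the proportion of participants with CR will be estimated using the Clopper-Pearson method".
- The Protocol Synopsis (Statistical Methods) says the rate of best response "of CR as determined by investigator assessment, will be estimated with 95% CI".
- SAP 3.2, headed Control of Type I Error, contains only this: "Unless otherwise specified, all CIs provided will be at the 95% confidence level".
- The SAP section "7.1. Efficacy Hypotheses" is marked as not applicable.
- Protocol 4.2 says that no comparison with historical controls will be made.

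SAP 9.1, which lists departures from protocol-defined analyses, mentions only the efficacy evaluable population. The SAP was written against Amendment 5 and, under SAP 2.1, carries over to later amendments. The current Protocol (Amendment 6) still contains 9.3.

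**The concern.** A significance level that names the primary endpoint, with a side and a value, reads like a decision rule. A 95% interval normally puts 2.5% in each tail, so its lower limit corresponds to a 1-sided 2.5% test. A 1-sided 5% level is twice as permissive. If both were live, the same data could pass on one and fail on the other, and the more lenient reading could be chosen once the results were known. The SAP neither adopts the level nor records that it is unused, so a reader might suspect an unrecorded change. At stake would be the error rate behind any claim that the CR rate exceeds 15%.

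**Working it through.** **Inputs.** From Protocol 9.2 and SAP 3.3: planned n = 46, assumed rate 35%, benchmark 15%, 10% loss. From Protocol 9.4.1.1 and SAP 7.2.1: Clopper-Pearson limits. From Protocol 9.3: 1-sided 5%. Neither document says that the 95% interval is two-sided; that is the conventional reading and is assumed here.

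**Formulas.** The exact lower limit for x responders out of n is L(x, n, a), the a-quantile of the Beta(x, n − x + 1) distribution. A two-sided 95% interval uses a = 0.025; a 1-sided 5% level uses a = 0.05. The cut-off r is the smallest x with L > 0.15. The probability of reaching it is P(X ≥ r) with X binomial(n, p).

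**1. Reproduce the plan's own figure.** 46 × 0.90 = 41.4, about 41 evaluable. With a = 0.025, L(11, 41) = 14.2% and L(12, 41) = 16.1%, so r = 12 and P(X ≥ 12 | 41, 0.35) = 82.4%. This meets the stated >80%. At n = 40 the probability is 79.5%; from n = 41 it stays above 80% (checked to n = 69). Also 41 / 0.9 = 45.6, which rounds up to 46. The sizing is therefore reproduced from a two-sided 95% interval with no use of 9.3.

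This does not prove which level was intended. With a = 0.05, n = 41 needs 11 CRs and gives 89.8%, also above 80%. The calculation also removes the 10% lost from the denominator. If they stay in as non-responders, the effective rate is 0.35 × 0.90 = 31.5%, and at n = 46 the probabilities are 73.2% (two-sided 95%) and 82.8% (1-sided 5%). How losses are handled is a separate question about 9.2, and the sizing criterion in 9.2 is an interval criterion either way.

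**2. Where could the two levels give different answers?** Treat 15% as a null, for illustration only.

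| n = 46 | Two-sided 95% CI (a = 0.025) | 1-sided 5% (a = 0.05) |
|---|---|---|
| L at 12 CRs (26.1%) | 14.3% | 15.8% |
| Cut-off r | 13 (L = 16.0%) | 12 |
| P(X ≥ r) at 15% | 1.53% | 3.54% |
| P(X ≥ r) at 35% | 86.8% | 92.5% |

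They disagree only at exactly 12 CRs. Its probability is 92.54% − 86.81% = 5.7% at a true rate of 35%, and 3.54% − 1.53% = 2.0% at 15%.

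Protocol 1.3.2 reports 47 treated participants by 16 APR 2023. At n = 47 the disagreement is again only at 12 CRs (13.9% against 15.4%; 1-sided p = 0.041), with probability 93.8% − 88.8% = 5.0% at 35%.

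SAP 5.3.1 defines a narrower population for the FDA submission, and its size is not given. Over an assumed range of n = 30 to 50, the cut-offs differ by one CR at every n except 34 and 39, where they coincide. Where they differ, the probability of landing on that one count at a true rate of 35% runs from 4.3% (n = 48) to 13.3% (n = 30).

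**3. Does any planned output use the level?** Neither Protocol 9.4.1.1 nor SAP 7.2.1 plans a p-value, a 1-sided bound or a success rule for the primary endpoint. The corresponding SAP display (Table 2.1.1 in Appendix C) is listed as a summary of response rates. The differences in step 2 therefore belong to a test that is not in the plan.

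**The case for a change.** The strongest opposing case is that a protocol should not carry a primary-endpoint error rate that its analysis does not use. With 12 CRs out of 46, a report could cite 9.3, quote a 1-sided p of 0.035 against 15%, and claim success while the 95% interval (14.3% to 41.1%) still contains 15%. In a smaller FDA population the chance of such a borderline count could be higher. One line in SAP 9.1 would close this off at almost no cost.

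Part of this stands. Section 9.3 is current text, nothing uses it, and the SAP does not say so. The arithmetic is also right.

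The step from unused to conflicting does not stand. An interval for estimation and a level attached to no test are different quantities. They collide only if the lower limit is read as a test against 15%. The plan uses 15% to choose the sample size and never declares it a null; SAP 7.1 and Protocol 4.2 both point away from such a test. Quoting a p-value of that kind would add an unplanned analysis, and the planned interval would still be reported beside it. The absence of an entry in SAP 9.1 is also defensible: that section records changed analyses, and the primary analysis is the same in both documents. Replacing 5% with 1-sided 2.5% against 15% would go further and add a decision rule that this estimation plan does not have.

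**Conclusion.** No change is called for. Protocol 9.3 is a clerical leftover: a level with no hypothesis to govern. An analyst following either document produces the same estimate and the same 95% Clopper-Pearson interval, and SAP 3.2 and 7.1 leave no room to apply 1-sided 5%. The effect on n, the CR estimate, its interval and the sizing criterion is nil. The illustrative difference, were 15% a null, is one CR: 12 against 13 of 46.

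This rests on two assumptions: that the 95% interval is two-sided, as is usual and as the reproduced sizing favours without proving; and that the primary result is reported as planned, by estimation. If the 95% limit were instead meant as a 1-sided bound, it would match 9.3 exactly and there would be no mismatch at all. The conclusion would change only if a formal test against 15% were added to the plan, because the level would then decide an outcome.
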